13.2.3 Laboratory Abnormalities as Adverse Events

Many laboratory abnormalities observed during the course of a study will be included under a reported adverse event describing a clinical syndrome (e.g., elevated BUN and creatinine in the setting of an adverse event of renal failure, or decreased hemoglobin in a case of bleeding esophageal varices). In such cases, the laboratory abnormality itself (e.g., elevated creatinine in a setting of renal failure) does not need to be recorded as an adverse event. However, isolated laboratory abnormalities should be reported as adverse events if they are considered to be

Title: A Multicenter, Double-Blind, Randomized Trial of IDN-6556 in Subjects Who had Hepatitis C Virus (HCV) Reinfection and Liver Fibrosis or Cirrhosis following Orthotopic Liver Transplantation for Chronic HCV Infection and Who Subsequently Achieved a Sustained Virologic Response Following anti-HCV Therapy

clinically significant by the Investigator. Criteria for a “clinically significant” laboratory abnormality are:

- a) A laboratory abnormality that leads to a dose-limiting toxicity (e.g., an abnormality that results in study drug dose suspension or discontinuation), or
- b) A laboratory abnormality that results in any therapeutic intervention (i.e., concomitant medication or therapy)

For laboratory abnormalities that do not meet the above criteria but are outside of normal range (e.g., < or > normal reference range), the Investigator should indicate whether the value is clinically significant (CS) or not clinically significant (NCS) for the subject.

13.3 Severity of Adverse Events

The Investigator must categorize the severity of each adverse event according to the following guidelines:

Mild: Associated with no limitation of usual activities or only slight discomfort; generally not requiring alteration or cessation of study drug administration; and/or not needing therapeutic intervention.

Moderate: Associated with limitation of usual activities or significant discomfort; generally requiring alteration or cessation of study drug administration; and/or requiring therapeutic intervention.

Severe: Associated with inability of subject to carry out usual activities or very marked discomfort; considered to be life-threatening; resulting in significant disability or incapacity; and requiring therapeutic intervention.

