- A persistent or significant incapacity or substantial disruption of the ability to conduct normal life functions
- A congenital anomaly/birth defect

Important medical events that may not result in death, be life-threatening, or require hospitalization may be considered serious when, based upon appropriate medical judgment, they may jeopardize the subject and may require medical or surgical intervention to prevent one of the outcomes listed in this definition. Examples of such medical events include allergic bronchospasm requiring intensive treatment in an emergency room or at home, blood dyscrasias or convulsions that do not result in inpatient hospitalization, or the development of drug dependency or drug abuse.

An adverse event or suspected adverse reaction is considered “life-threatening” if, in the view of either the Investigator or sponsor, its occurrence places the subject at immediate risk of death. It does not include an adverse event or suspected adverse reaction that, had it occurred in a more severe form, might have caused death.

An adverse event or suspected adverse reaction is considered ‘unexpected’ if it is not listed in the Investigator’s Brochure or is not listed at the specificity or severity that has been observed; or, if an Investigator’s Brochure is not required or available, is not consistent with the risk information described in the general investigational plan or elsewhere in the current application. For example, under this definition, hepatic necrosis would be unexpected (by virtue of greater severity) if the Investigator’s Brochure referred only to elevated hepatic enzymes or hepatitis. Similarly, cerebral thromboembolism and cerebral vasculitis would be unexpected (by virtue of greater specificity) if the Investigator’s Brochure listed only cerebral vascular accidents. ‘Unexpected,’ as used in this definition, also refers to adverse events or suspected adverse reactions that are mentioned in the Investigator’s Brochure as occurring with a class of drugs or as anticipated from the pharmacological properties of the drug, but are not specifically mentioned as occurring with the particular drug under investigation.

Title: A Multicenter, Double-Blind, Randomized Trial of IDN-6556 in Subjects Who had Hepatitis C Virus (HCV) Reinfection and Liver Fibrosis or Cirrhosis following Orthotopic Liver Transplantation for Chronic HCV Infection and Who Subsequently Achieved a Sustained Virologic Response Following anti-HCV Therapy

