11.2 ADVERSE EVENTS

The incidence of TEAEs will be summarized descriptively by treatment group for the following:

- system organ class (SOC) and preferred term
- SOC, preferred term, and severity
- SOC and preferred term for TEAEs classified as related to study drug
- SOC and preferred term for events having incidence of $\geq 5\%$ in any treatment group
- SOC and preferred term for subjects with study discontinuation due to the AE
- SOC and preferred term for subjects with study drug interruption due to the AE
- preferred term (alphabetical and highest incidence in all emricasan dose groups)

Missing values for severity, relationship to study drug, action taken with study drug, treatment required, and/or outcome will be summarized as unknown.

The incidence of SAEs for each SAE will be summarized descriptively by treatment group and overall for the following:

- SOC and preferred term
- SOC, preferred term, and severity
- SOC and preferred term for SAEs classified as related to study drug
- preferred term (alphabetical and highest incidence in all emricasan dose groups)

Subject listings by unique subject number and visit will be provided for the listings below:

- All AEs
- Subjects who discontinued from the study
- Subjects who had a study drug interruption
- Subjects with SAEs
- Subjects who died

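### Read literally, Protocol 13.3 grades an event Severe only if it is also life-threatening, disabling and treated, so the severity tables could under-count Severe events or be inconsistent

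*Protocol*

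**What the plan says.** Protocol 13.3 makes grading mandatory but calls its definitions guidelines: "The Investigator must categorize the severity of each adverse event according to the following guidelines". The three grades are built as follows.

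- **Mild** ends "generally not requiring alteration or cessation of study drug administration; and/or not needing therapeutic intervention".
- **Moderate** begins "Moderate: Associated with limitation of usual activities or significant discomfort" and ends "generally requiring alteration or cessation of study drug administration; and/or requiring therapeutic intervention".
- **Severe** begins "Severe: Associated with inability of subject to carry out usual activities or very marked discomfort" and continues "considered to be life-threatening; resulting in significant disability or incapacity; and requiring therapeutic intervention".

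Protocol 13.2 defines seriousness separately. Life-threatening and significant incapacity are both on its list of serious outcomes. An event is life-threatening there when "its occurrence places the subject at immediate risk of death".

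The SAP does not redefine severity. SAP 11.2 tabulates both treatment-emergent adverse events and serious adverse events by "SOC, preferred term, and severity". Protocol 12.6.2 also promises a description of the intensity of adverse events.

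**The concern.** Severe is the only grade whose list ends in a plain *and*. A semicolon list closed in that way ordinarily requires every item. Protocol 13.4, the next section, also uses *and/or* in several of its causality categories, so the authors had that connector to hand when they meant alternatives.

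On the literal reading, an event that stops all usual activity but carries no immediate risk of death is not Severe. Two of the four items also largely repeat seriousness criteria from 13.2, which ties severity to a scale that the protocol otherwise keeps apart from it.

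At stake is what the severity tables mean. Safety and tolerability is a secondary objective, and these tables are where a reader looks for the burden of severe events. About 60 subjects are spread over about 35 sites, or 60/35 = 1.7 per site. If sites differ in how they read the list, there is little within-site experience to smooth that out.

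**Working it through.** The plan gives no figure to reproduce, so the check is a reading of the definitions with a hand count of cases.

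**Step 1. The items in Severe (Protocol 13.3).**

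- A: unable to do usual activities, or very marked discomfort
- B: life-threatening
- C: disabling
- D: needs treatment

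**Step 2. Count the combinations.** Four yes/no items give 2^4 = 16 combinations. These are logical cases, not probabilities, and some will be rare in practice.

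| Rule for Severe | Combinations graded Severe |
|---|---|
| A and B and C and D (literal) | 1 of 16 |
| A or B or C or D (*and/or* throughout) | 16 − 1 = 15 of 16 |
| A alone sufficient; B and C not required; D alone not enough | all 8 with A |

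**Step 3. Where the incapacitating or very uncomfortable events go under the literal rule.** Of the 8 combinations with A present, 1 is Severe and 7 are not.

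- In 3 of the 7, D is present. These meet the treatment item of Moderate.
- In the other 4, D is absent. These reach Moderate only if being unable to do usual activities counts as being limited in them (or very marked discomfort as significant discomfort), or if study drug is changed or stopped. Otherwise they fit no grade cleanly.

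**Step 4. What *and/or* alone would do.** D is present in 8 of the 16 combinations. All 8 would qualify as Severe, because D alone would be enough. All 8 also meet the treatment item that Moderate already lists as an alternative. The two grades would overlap for every treated event.

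**Step 5. What depends on the grade.** SAP 11.2 has one severity breakdown for treatment-emergent events and one for serious events, both descriptive. The seriousness definition (Protocol 13.2), the 24-hour reporting rule (13.5.2), dose interruption (13.1), liver follow-up (8.1.9) and the three-category decision guideline (SAP 4) do not refer to it.

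**Step 6. Scale.** With the planned arms, one subject regraded moves the severe-event rate by 1/20 = 5 percentage points on placebo, or 1/40 = 2.5 points on emricasan. This holds for any single misclassified subject in any yes/no table. It shows how coarse the tables are and does not estimate the effect of this wording.

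**The case against.** The best defence is that the definitions are offered as guidelines, so an investigator may treat the Severe list as descriptors and grade by judgement. That is fair, and it means under-counting is not certain. It does not remove the problem: nothing tells sites to read *and* as *or*, and if some do and others do not, the same event gets two grades.

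A second defence is that safety capture does not rest on severity. This stands. Many incapacitating events would be serious under 13.2. They would be reported within 24 hours, tabulated by system organ class and preferred term whatever their grade, and listed.

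Third, grading is done under the blind, so nothing suggests that the wording favours one arm. This also stands. The weakness is in the level and consistency of the Severe counts, with no evident bias in the comparison.

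A reader might infer more: that truly severe events are moved to Moderate, or that the Severe rows will contain only life-threatening events. The documents do not support either as fact. The protocol does not say where such events go. Step 3 shows that some have no clear grade, and investigators who read the list as alternatives would still record Severe.

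**Conclusion.** The point holds as a wording defect in an operational rule. Protocol 13.3, applied literally, keeps incapacitating events that are not life-threatening out of the Severe grade, and neither document corrects it. The consequence is conditional. If sites follow the text, Severe is under-counted; if they differ, grading is inconsistent; if all read the list as alternatives, Severe events are not under-counted for this reason, but treated events can meet both Moderate and Severe.

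The size cannot be computed, because the documents give no event rates and no information on how sites read the list. The effect is confined to the descriptive severity summaries. It does not reach the reporting of serious events, the primary endpoint or the decision guideline's response-rate thresholds. It is worth correcting because the repair is specific and cheap.

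**What to change.** Reword Severe in Protocol 13.3 to say three things:

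1. Being unable to do usual activities, or very marked discomfort, is sufficient for Severe.
2. Life-threatening and disabling are not required. They are seriousness criteria and are recorded under 13.2.
3. Need for treatment alone does not make an event Severe, since Moderate already covers it.

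Do not simply replace the final *and* with *and/or*, for the reason in Step 4.

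The cost is a protocol clarification, which Protocol 14.1 requires to be submitted to the IRB/IEC, and a note in the CRF completion guide for about 35 sites. Events already graded under the present wording should be checked, and regraded where needed before unblinding, so that the SAP 11.2 tables do not mix two definitions. No procedure, sample size or analysis method changes.

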13.4 Classification of Adverse Events by Relationship to Study Drug Administration

The Investigator must assess whether each adverse event is related to either IDN-6556 or placebo. The relationship of each adverse event will be assessed by the Investigator after careful consideration, and according to the following guidelines:

Definitely: A reaction that follows a reasonable temporal sequence from administration of study drug; that follows a known or expected response pattern to the study drug; it disappears or decreases on

Title: A Multicenter, Double-Blind, Randomized Trial of IDN-6556 in Subjects Who had Hepatitis C Virus (HCV) Reinfection and Liver Fibrosis or Cirrhosis following Orthotopic Liver Transplantation for Chronic HCV Infection and Who Subsequently Achieved a Sustained Virologic Response Following anti-HCV Therapy

cessation or reduction in study drug dose; and/or it reappears or worsens when the study drug is administered.

Probably: A reaction that follows a reasonable temporal sequence from administration of study drug; that follows a known or expected response pattern to the study drug; and/or that could not be reasonably explained by other factors such as underlying disease, complications, concomitant drugs, or concurrent treatments.

Possibly: A reaction that follows a reasonable temporal sequence from administration of study drug; that follows a known or expected response pattern to the study drug, but that could reasonably have been produced by a number of other factors including underlying disease, complications, concomitant drugs, or concurrent treatments.

Unlikely: A reaction that does not follow a reasonable temporal sequence from administration, and/or that can be reasonably explained by other factors, including underlying disease, complications, concomitant drugs, or concurrent treatments.

Not Related: A reaction for which sufficient data exist to indicate that the etiology is unrelated to the study drug.

13.5 Recording and Reporting Adverse Events

13.5.1 Recording Adverse Events

All adverse events will be recorded in the appropriate section of the case report form. Subjects withdrawn from the study due to adverse events will be followed by the Investigator until the outcome is determined and, when appropriate, additional written reports and documentation will be provided. The Investigator should attempt, if possible, to establish a diagnosis based on the presenting signs and symptoms.

If the adverse event meets the definition of a serious adverse event, or if the Investigator becomes aware of an unexpected adverse event that places the subject at risk or a pregnancy at any time after the study drug administration up to the end of the study follow-up period, the event must be documented and reported as described in **Section 13.5.2**.

Title: A Multicenter, Double-Blind, Randomized Trial of IDN-6556 in Subjects Who had Hepatitis C Virus (HCV) Reinfection and Liver Fibrosis or Cirrhosis following Orthotopic Liver Transplantation for Chronic HCV Infection and Who Subsequently Achieved a Sustained Virologic Response Following anti-HCV Therapy

13.5.2 Investigator Reporting of a Serious Adverse Event

In agreeing to the provisions of this protocol, the Investigator accepts all legal responsibilities for prompt notification of serious adverse events to the Sponsor's Medical Monitor or designee.

All serious adverse events must be reported to Conatus within 24 hours after the Investigator recognizes/classifies the event as a serious adverse event. At a minimum the following information should be provided at the time of the initial report: subject number and initials, a description of the event, at least one criterion classifying the event as Serious and the name and title of the reporting individual. Additionally, judgment of causality by the Investigator must be provided as soon as possible to ensure timely reporting to regulatory authorities by the Sponsor or designee(s) (e.g., CIOMS forms, FDA MedWatch Form 3500A or other equivalent form). After the initial report, as necessary, the Investigator must provide any additional information on a serious adverse event to the Medical Monitor within 24 hours after he/she receives that information. This follow-up information will be a detailed written report that will include copies of hospital records, case reports, autopsy reports, and other pertinent documents.

Conatus will consider the Investigator's assessment of the causality assessment; however, since Conatus will assess the overall safety of the study medication, Conatus' causality assessment will take precedence, unless the Investigator's assessment must take precedence per country-specific regulations

Contact:

SyneractHCR Safety
Safety [contact]
[contact]

OR
if not available

[name]
VP, Pharmacovigilance
[contact]
[contact]
[contact]

All serious adverse events must be reported to Conatus within 24 hours after the Investigator recognizes/classifies the event as a serious adverse event. At a minimum the following information should be provided at the time of the initial report: subject number and initials, a description of the event, at least one criterion classifying the event as Serious and the name and title of the reporting individual. Additionally, judgment of causality by the Investigator must be provided as soon as possible to ensure timely reporting to regulatory authorities by the Sponsor or designee(s) (e.g., CIOMS forms, FDA MedWatch Form 3500A or other equivalent form). After the initial report, as necessary, the Investigator must provide any additional information on a serious adverse event to the Sponsor or designee within 24 hours after he/she receives that information. This follow-up information will be a

Title: A Multicenter, Double-Blind, Randomized Trial of IDN-6556 in Subjects Who had Hepatitis C Virus (HCV) Reinfection and Liver Fibrosis or Cirrhosis following Orthotopic Liver Transplantation for Chronic HCV Infection and Who Subsequently Achieved a Sustained Virologic Response Following anti-HCV Therapy

detailed written report that will include copies of hospital records, case reports, autopsy reports, and other pertinent documents.

Conatus will consider the Investigator's assessment of the causality assessment; however, since Conatus will assess the overall safety of the study medication, Conatus' causality assessment will take precedence, unless the Investigator's assessment must take precedence per country-specific regulations

13.6 Additional Investigator Responsibilities on Follow-up of Serious Adverse Events

The Investigator and supporting personnel responsible for subject care should discuss with the Medical Monitor any need for supplemental investigations of serious adverse events. The results of these additional assessments conducted must be reported to Conatus. If a subject dies during participation in the study and a post-mortem examination is performed, a copy of the autopsy report must be submitted to Conatus.

13.7 Post-Study Follow-Up of Adverse Events

All adverse events, including a worsening of clinically significant laboratory values, physical examination findings compared with Baseline values, must be followed until the event resolves, the condition stabilizes, the event is otherwise explained, or the subject is lost to follow-up.

Adverse events ongoing at the final visit will be followed for as long as necessary to adequately evaluate the subject's safety or until the event stabilizes or resolves. If resolved, a resolution date should be documented on the case report form or reported to Conatus if the case report forms have been collected. The Investigator is responsible to ensure that follow-up includes any supplemental investigations as may be indicated to elucidate the nature and/or causality of the adverse event. This may include additional laboratory tests or investigations, histopathological examinations, or consultation with other health care professionals as is practical.

13.8 Notification of Post-Study Serious Adverse Events

Investigators are not obligated to actively follow subjects after the completion of the study. However, if the Investigator becomes aware of a serious adverse event, he/she should notify Conatus if such an event is attributable to study drug. The notification to Conatus of a post-study serious adverse event by the Investigator should occur within 24 hours of becoming aware of the serious adverse event.

Title: A Multicenter, Double-Blind, Randomized Trial of IDN-6556 in Subjects Who had Hepatitis C Virus (HCV) Reinfection and Liver Fibrosis or Cirrhosis following Orthotopic Liver Transplantation for Chronic HCV Infection and Who Subsequently Achieved a Sustained Virologic Response Following anti-HCV Therapy

13.9 IRB/IEC Notification of Serious Adverse Events

The Investigator is responsible for promptly notifying her/his IRB/IEC of all serious adverse events, including any follow-up information, occurring at her/his site. In addition, the Investigator is responsible for submitting information on SUSARs/SAEs received from Conatus to their local IRB/IEC. Documentation of the submissions to IRBs/IECs must be retained in the appropriate study file(s).

However, in some countries, the notification of SUSARs/SAEs to IRB/IEC will be the responsibility of the Sponsor or the Sponsor's designee.

13.10 Health Authority Safety Reports

Conatus, or its representatives, will submit a safety report to the US Food and Drug Administration (FDA) and any other appropriate regulatory agencies in accordance with country specific requirements, for any serious adverse event that is unexpected and related to the study drug within the appropriate time frame. Conatus or its representatives will send copies of each safety report submitted to the FDA and other regulatory agencies to the Investigators who are actively participating in Conatus-sponsored clinical studies. Safety reports must be submitted to the appropriate IRB/IEC as soon as possible. In some countries, submission of the safety reports to IRB/IEC will be made by Conatus or its representatives. Documentation of the submission to the IRB/IEC must be retained for each safety report. As instructed by Conatus or its designee, safety reports should be retained in the appropriate study files, or with the Investigator's Brochure.

